10.2.4.2 Duration of Response

Duration of Response is defined as the time between the earliest date of CR or PR response and the date of the first occurrence of PD or death and calculated as:

$(date\ of\ first\ PD/death - date\ of\ first\ CR/PR + 1) / 30.4375.$

Censoring rules for PFS will be applied to DoR. The DoR will be estimated for all evaluable subjects who achieve an objective response of PR or CR.

The sensitivity analyses for PFS will also be reproduced for DoR.

10.2.4.3 Time to Response

Time to response is defined as the time from the date of the first dose until the date of first CR or PR. It is calculated as:

$(date\ of\ first\ CR/PR - date\ of\ first\ Debio\ 1562\ dose + 1) / 30.4375.$

Time to response will be estimated for all evaluable subjects who achieve an objective response of PR or CR. No subject censoring is involved.

Time to complete response is defined as the time from the date of the first dose until the date of first CR. It is calculated as:

$(date\ of\ first\ CR - date\ of\ first\ Debio\ 1562\ dose + 1) / 30.4375.$

Time to complete response will be estimated for all evaluable subjects who achieve an objective response of CR. No subject censoring is involved.

10.2.4.4 Overall Survival

Overall Survival is defined as the time between the date of the first dose and the date of death. It is calculated as:

$(date\ of\ death - date\ of\ first\ Debio\ 1562\ dose + 1) / 30.4375.$

Subjects who do not experience the event of death will be right-censored at their last date known to be alive as 'Ongoing' or 'Lost to follow-up'.

The date of attempted contact, survival status and - if new anti-cancer therapy was started - along with the respective regimen will be listed.

The following sensitivity analyses will be performed:

1. An additional analysis will be done by censoring the Cohort B subjects who have switched to Q3W regimen at their last assessment date while they were still in QW regimen
2. An additional analysis will be done by censoring the subjects who died due to Covid-19 at their death date, instead of considering that they died

[REDACTED]

[REDACTED]

[REDACTED]

[figure not shown]
[REDACTED]

[figure not shown]
Clinical study Debio 1562-201
Statistical Analysis Plan
Version 3.1 dated 2021-05-07

[figure not shown]
VV-TMF-82056 | Page 33/83

Page 33 of 82

Debiopharm International S.A.

10.3 Safety Analyses

All safety analyses will be conducted on the safety population. All summaries will present data by cohort, unless otherwise specified. Safety evaluations will be based on the incidence and severity of adverse events (AEs), clinically significant changes or abnormalities in the subject's laboratory results, vital signs, physical examination, ECG, and Eastern Cooperative Oncology Group (ECOG) score.

10.3.1 Adverse Events

An AE is any noxious, pathologic, or unintended change in anatomical, physiologic, or metabolic function as indicated by physical signs, symptoms, or laboratory changes occurring in any phase of a clinical study, whether or not considered study drug-related. This includes an exacerbation of a pre-existing condition.

An AE will be considered to be a treatment-emergent adverse event (TEAE) if it begins or worsens on or after the first dose date of either Debio 1562 or rituximab, whichever occurs first, and before the last dose date of either Debio 1562 or rituximab + 30 days, whichever occurs last.

A serious adverse event (SAE) is defined as any event that results in death, is life threatening, requires inpatient hospitalization or prolongation of existing hospitalization, results in persistent or significant disability/incapacity or substantial disruption of the ability to conduct normal life functions, results in a congenital anomaly/birth defect, or may jeopardize the patient and require medical or surgical intervention to prevent one of the outcomes listed in this definition.

Adverse events will be coded with the Medical Dictionary for Regulatory Activities (MedDRA; version 19.0 or later) and summarized per system organ class (SOC) and preferred term (PT). Severity grade will be defined according to the National Cancer Institute (NCI) common terminology criteria for adverse events (CTCAE) v4.03.

A study drug related AE is an event where the investigator determined that the relationship to study drug (evaluated separately for Debio 1562 and rituximab) was "possibly related", "probably related", or "definitely related".

[figure not shown]
Only missing AE onset dates will be imputed as shown in Appendix I. Adverse events for which onset date could not be determined after imputation of missing date are considered to be treatment emergent.

Adverse events will be summarized per SOC, PT, and CTCAE grade. For summaries by relationship, adverse events with missing relationship are counted as "Possibly Related". Adverse events with missing CTCAE grade will not have CTCAE grade imputed. In tabulations, however, if the subject has at least one PT with a non-missing CTCAE grade, the non-missing grade will be displayed.

In addition, the following groups of terms will be analyzed in a grouped manner:

- Neutrophil count decreased (PT Code 10029366) and Neutropenia (PT Code 10029354)

- Lymphocyte count decreased (PT Code 10025256) and Lymphopenia (PT Code 10025327)
- White blood cell count decreased (PT Code 10047942) and Leukopenia (PT Code 10024384)
- Platelet count decreased (PT Code 10035528) and Thrombocytopenia (PT Code 10043554)
- Blood magnesium decreased (PT Code 10005654) and Hypomagnesaemia (PT Code 10021027)
- Oxygen saturation decreased (PT Code 10033318) and Hypoxia (PT Code 10021143)
- Pneumonia (PT code 10035664) and lung infection (PT Code 10061229)

Treatment emergent adverse events will be summarized by the total number of events and CTCAE grade. TEAEs will also be summarized by the number of subjects with at least one event and will be grouped by SOC, PT, and CTCAE grade. In all tables, a subject contributes only once to the count for a given AE (SOC or PT) at the worst CTCAE grade. Each subject will contribute only once for the most related occurrence or the most intense occurrence to each of the incidence rates in the descriptive analysis, regardless of the number of episodes, e.g. worst grade per subject per AE (except for total number of events). All summary tables will be grouped by cohorts defined at Section 9.1 and overall.

Besides the overall summary of all TEAEs, the following summaries of TEAEs by system organ class, preferred term, and CTCAE grade will be provided:

- All TEAEs;
- All Grade 3 or higher TEAEs;
- All treatment-related TEAEs (overall and by cohort and study treatment);
- All treatment-related Grade 3 or higher TEAEs (overall and by cohort and study treatment);
- All serious TEAEs;
- All treatment-related serious TEAEs (overall and by cohort and study treatment);
- All TEAEs excluding serious;
- All TEAEs resulting in treatment discontinuation (overall and by cohort and study treatment);
- All TEAEs leading to death;
- All dose-modifying events;

The following summaries of TEAEs by preferred term and CTCAE grade will be provided:

- TEAEs with at least 10% overall incidence (tables and figures)
- Treatment-related TEAEs with at least 10% overall incidence (overall and by cohort and treatment, tables and figures)

As a subgroup analysis, the overall summary of all TEAEs will be done for subjects with a treatment duration inferior or equal to 6 cycles versus for subjects with a treatment duration greater than 6 cycles.

Data listings will be provided for all AEs, SAEs, study drug related AEs, AEs resulting in study drug discontinuation, AEs considered as being dose-modifying events and AEs leading to death. Relationship to Debio 1562 or rituximab, and action taken regarding Debio 1562 and/or rituximab administration, respectively will be provided. Non-TEAEs will be flagged in the listings.

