Appendix I. **EASTERN COOPERATIVE ONCOLOGY GROUP (ECOG) PERFORMANCE STATUS SCALE (OKEN, 1982)**

Grade	Scale
0	Fully active, able to carry out all pre-disease performance without restriction. (Karnofsky 90-100)
1	Restricted in physically strenuous activity but ambulatory and able to carry out work of a light or sedentary nature, e.g., light housework, office work. (Karnofsky 70-80)
2	Ambulatory and capable of all self-care but unable to carry out work activities. Up and about more than 50% of waking hours. (Karnofsky 50-60)
3	Capable of only limited self-care, confined to bed or chair more than 50% of waking hours. (Karnofsky 30-40)
4	Completely disabled. Cannot carry on any self-care. Totally confined to bed or chair. (Karnofsky 10-20)

Adverse Event

- If onset date is completely missing:
 - o If AE end date is missing or on/after the date of first dose, then onset date is set to date of first dose
 - o If AE end day is missing, but the month and year of the AE end date is larger than the month and year of the first dose date, then the onset date is set to the date of first dose
 - o If AE end month is missing, but the year of the AE end date is larger than the year of the first dose date, then the onset date is set to the date of first dose
 - o If AE end date is prior to the date of the first dose, then onset date is not imputed
- If (onset year is present and month and day are missing) or (onset year and day are present and month is missing):
 - o If year = year of first dose, then set onset month and day to month and day of first dose
 - o If year < year of first dose, then set onset month and day to December 31st.
 - o If year > year of first dose, then set onset month and day to January 1st.
- If onset month and year are present and day is missing:
 - o If year=year of first dose and
 - If month = month of first dose then set day to day of first dose date
 - If month < month of first dose then set day to last day of month
 - If month > month of first dose then set day to 1st day of month
 - o If year < year of first dose then set day to last day of month
 - o If year > year of first dose then set day to 1st day of month
- For all other cases, set onset date to date of first dose

Concomitant Medications

- If start date is completely missing or year is missing then start date will not be imputed.
- If start year is present and month and day are missing then set start month and start day to January 1.

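### The SAP date rules can class an adverse event that ended before first dose as treatment-emergent when its onset date is missing or partial

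*SAP*

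**What the plan says.** SAP 10.3.1 defines a TEAE as an event that "begins or worsens on or after the first dose date of either Debio 1562 or rituximab, whichever occurs first", with an upper limit of 30 days after the last dose. The same section sends the programmer to the imputation rules ("Only missing AE onset dates will be imputed as shown in Appendix I") and then gives the default: "Adverse events for which onset date could not be determined after imputation of missing date are considered to be treatment emergent".

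Appendix I is the ECOG scale. SAP 8.1, 9.1 and the table of contents place the date rules in Appendix J. The Adverse Event block there contains these branches:

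- Onset completely missing, event over before dosing: "If AE end date is prior to the date of the first dose, then onset date is not imputed".
- Onset month missing: "If year = year of first dose, then set onset month and day to month and day of first dose".
- Onset day missing, year equal to that of first dose: "If month = month of first dose then set day to day of first dose date", and "If month < month of first dose then set day to last day of month".
- Closing rule: "For all other cases, set onset date to date of first dose".

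A condition that imputed dates must agree with the rest of the database appears in Appendix J for death and progression dates. None is stated for adverse event onset.

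**The concern.** An event that was over before the first infusion can neither start nor worsen after it, so by definition it is not a TEAE. Where the recorded end date settles the timing, a default meant for unknown timing should not override it.

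Such events are in the database: Protocol 9.1 has adverse events recorded from informed consent. TEAE incidence is a primary endpoint (SAP 3.1), and the flag feeds the TEAE tables in 10.3.1, including the Grade 3 or higher, serious and treatment-related summaries. Under 10.3.1 a missing causality assessment is counted as possibly related, so a pre-dose event could also enter a treatment-related table. The listings mark events that are not treatment-emergent, so they would carry the same wrong flag.

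**Working it through.** The plan gives no figure to reproduce. The check follows the rules through single records and then shows how far they reach.

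**Route (a): onset completely missing.** Appendix J leaves the onset blank when the end date precedes first dose. Every other unresolved case goes to the first-dose date under the closing rule. The set with no onset after imputation is therefore exactly the set known to have ended before dosing, and the 10.3.1 default makes all of it treatment-emergent. A partial end date that is clearly earlier (end April, first dose 20 May) gives the same class on either reading: not imputed leads to the default, and the closing rule gives the first-dose date.

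**Route (b): partial onset.** The same-year and same-month branches set onset to the first-dose date without consulting the end date. The imputed onset can then fall after resolution. This route does not need the 10.3.1 default.

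**Worked records.** First dose 20 May 2019, event ended 10 May 2019:

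| Recorded onset | Onset after Appendix J | Class | Correct? |
|---|---|---|---|
| Missing | Not imputed | TEAE by 10.3.1 default | No |
| 2019 | 20 May 2019 | TEAE | No |
| May 2019 | 20 May 2019 | TEAE | No |
| April 2019 | 30 April 2019 | Not TEAE | Yes |
| 2018 | 31 December 2018 | Not TEAE | Yes |
| 5 May 2019 | Unchanged | Not TEAE | Yes |

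**Reach of the rules.** Assumptions: the event starts and ends 1 to W days before first dose, all onset/end pairs are equally likely, the end date is complete, and first dose is uniform over a 365-day year. W = 28 is an assumption, taken from the 28-day screening window in the schedules of events.

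- Pairs for W = 28: 28 × 29 / 2 = 406. Over 365 first-dose days: 406 × 365 = 148,190 records for each type of onset.
- An onset s days before first dose can pair with s end dates, so the mean onset lag is Σs² / Σs = (2W + 1) / 3 = 57 / 3 = 19 days.
- Onset missing: all 148,190 are classed TEAE (100%).
- Month and day missing: wrong whenever onset and first dose share a year, (365 − 19) / 365 = 346 / 365 = 94.8% (140,476 records).
- Day missing: wrong whenever they share a month. An onset s days earlier falls in the previous month for 12s of the 365 first-dose days, so (365 − 12 × 19) / 365 = 137 / 365 = 37.5% (55,622 records).

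Direct enumeration of the coded rules gives the same counts. An onset with the day present and the month missing follows the same branch as year-only and also gives 94.8%.

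| Window W | Mean lag (days) | Month and day missing | Day missing |
|---|---|---|---|
| 28 days | 19 | 94.8% | 37.5% |
| 21 days | 43/3 | 96.1% | 52.9% |
| 14 days | 29/3 | 97.4% | 68.2% |
| 7 days | 5 | 98.6% | 83.6% |

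**The case against.** The strongest objection is about weight. An affected record must start and end between consent and first dose, have an end date good enough to prove it, and have an onset that is missing or partial in the wrong place. Protocol 11.13 has data reviewed against source and missing data explained, so few such records should survive. The error only overcounts. Safety is descriptive: SAP 10.2.1 limits hypothesis testing to the primary efficacy endpoint, and Protocol 10.6.3 plans no formal safety interim. All of this stands, and it keeps the expected effect small. It does not make the rule right.

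A second argument is intent. Appendix J deliberately separates events that ended before dosing, presumably to keep them out of the treatment period, so the default may have been meant only for unknown timing. That is plausible, but nothing in the text says so. The closing rule already resolves every case of unknown timing, which leaves the default nothing else to act on.

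Third, the percentages are calendar arithmetic on records already defined as pre-dose. That is fair, and they should not be read as trial impact. The 10.3.1 default also drives route (a) only; route (b) rests on Appendix J.

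Fourth, resetting an imputed onset to the end date could override a recorded day when only the month is missing. Appendix J already overwrites the recorded day in that branch, so the fix adds no new fault.

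One caveat remains: the Appendix J heading is missing from the public text I read, so the absence of a consistency condition for adverse events is shown only for the text that survives.

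**Conclusion.** The rules as written are wrong for a definable set of records. An event known to have ended before first dose becomes treatment-emergent in every case when its onset is completely missing, and whenever a partial onset shares the year (month missing) or the month and year (day missing) of first dose. Partial onsets in an earlier month or year, and complete onsets, are classified correctly.

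The conclusion about the rules follows from the text and needs no assumption. The percentages rest on the assumed window and equal weighting. The documents give no count of affected records, so no change in TEAE incidence is estimated. It is probably very small and can only be upward. The point deserves correction because the flag defines a primary endpoint and the recorded data already give the right answer. The wrong appendix reference in 10.3.1 is certain.

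**What to change.** Add one rule to SAP 10.3.1 and to the Adverse Event block of Appendix J:

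> For an AE with a missing or partial onset date, if the recorded complete or partial end date shows that it ended before the first dose of either drug, the AE is not treatment-emergent. A completely missing onset stays missing. A partial onset that would be imputed later than the end date is set to the end date or, if the end date is partial, to the last date it allows before first dose.

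Keep the conservative default where the end date is missing, falls on or after first dose, or does not settle the timing; for example, onset missing and end known only as May 2019 with first dose on 20 May 2019. Leave complete onset dates unchanged. Query any record whose recorded onset, complete or partial, is later than its end date, and do not reclassify it. Change the reference in 10.3.1 from Appendix I to Appendix J.

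Applied to the three onset types above (3 × 148,190 = 444,570 records), the rule leaves none misclassified and no imputed onset after its end date. The first result is true by construction. Partial end dates were tried only on single examples.

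The cost is one SAP rule stated in two places, a few conditions in the TEAE-flag program, one data check for onset later than end, and one corrected reference. No new data are needed.

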10.3.2 Deaths and Other Significant Adverse Events

The primary cause of death will be presented in a table with the following reasons: PD, AE, Other, or Unknown; also whether an autopsy was performed or not. Separate summaries of deaths occurring on-study or within 30 days of last dose of either Debio 1562 or rituximab, and deaths after 30 days of last dose of either Debio 1562 or rituximab will also be provided. All deaths occurring on-study and during follow-up will be presented in a listing; deaths occurring after 30 days of last dose of either Debio 1562 or rituximab will be flagged.

10.3.3 Clinical Laboratory Evaluations

Screening laboratory evaluations (hematology, clinical chemistry, urinalysis, and coagulation) may be performed within 28 days before the first dose. Repeat testing will be performed as outlined in schedule of events ([Appendix A](#), [Appendix B](#) and [Appendix C](#)) and as clinically indicated. Clinical laboratory results will be classified as Low, Normal, and High, or Normal/Abnormal according to the lab normal ranges, and will be graded according to NCI CTCAE, Version 4.03.

All hematology, serum chemistry, urinalysis, and coagulation will be listed per subject for each assessment and descriptive statistics will be tabulated for selected criteria detailed below by cohort and overall. SI units will be used for listing and reporting. Changes and percent changes from baseline in hematology and serum chemistry will be calculated for each subject and subsequently summarized by cohort and overall. Shifts from baseline in hematology and serum chemistry values will also be summarized by CTCAE grade within cohorts and overall. Only scheduled visits will be included in change from baseline summary tables; however, unscheduled visits will be included in worse post-baseline shift tables, liver function tests summaries, and listings.

10.3.3.1 Hematology

Hematology will include: hematocrit (HCT), hemoglobin (HGB), platelet count (PLAT), red blood cell (RBC) count, white blood cell (WBC) count with differential [i.e. neutrophils count (NEUT), lymphocyte (LYM), monocytes (MONO), eosinophils, and basophils (BASO)].

Shift from baseline to worst post-baseline low and high CTCAE grade for hematology parameters will be presented in a table for: HGB, RBC, NEUT, PLAT, LYM and WBC. In the

shift table based on being lower than a lower normal limit (worst low), a value above the upper normal limit will be considered as grade 0.

10.3.3.2 *Serum chemistry*

Serum chemistry will include: albumin (ALB), alkaline phosphatase (ALP), alanine aminotransferase (ALT), aspartate aminotransferase (AST), blood urea nitrogen (UREAN), calcium (CA), chloride (CL), creatinine (CREAT), glucose (GLUC), lactate dehydrogenase (LDH), magnesium (MG), phosphorus (PHOS), potassium (K), Sodium, total bilirubin (BILI), total protein (PROT), Uric acid (URATE), and Immunoglobulin levels (i.e., IgG, IgA, and IgM).

Shift from baseline to worst post-baseline CTCAE grade for serum chemistry parameters (i.e. ALB [worst low only], ALP, ALT, AST, CREAT, BILI, and URATE [worst high only], and PHOS, CA, CL, GLUC, MG, K, and SODIUM [both worst low and worst high]) will be presented in separate tables for CTCAE based on being higher or lower than normal limits, where applicable. In the shift table based on being higher than an upper normal limit (worst high) a value below the lower normal limit will be considered as grade 0. Likewise, in the shift table based on being lower than a lower normal limit (worst low), a value above the upper normal limit will be considered as grade 0.

10.3.3.3 *Urinalysis and Pregnancy Test*

Urinalysis includes: appearance, specific gravity, and pH. Microscopic examination of sediment is to be performed if the specimen is positive for WBCs, proteins, or blood. Semi quantitative evaluations include using dipsticks for glucose, protein, bilirubin, ketones, leukocytes and blood. Urinalysis and pregnancy test laboratory results will be presented in separate listings.

Coagulation

Coagulation tests include: prothrombin time, International Normalized Ratio (INR), and activated partial thromboplastin time (aPTT). Coagulation results will be presented in a data listing.

10.3.3.4 *Liver Function Test*

Clinically significant values in liver function tests will be summarized by the following categories using the maximum value while on treatment. The denominator for the summaries will be the number of subjects who had at least one non-missing value during treatment. Please note that the categories for each test are not mutually exclusive:

- AST:
 - o > 1xULN & ≤ 3xULN;
 - o > 3xULN & ≤ 5xULN;
 - o > 5xULN & ≤ 10xULN;
 - o > 10xULN & ≤ 20xULN;

- o > 20xULN;
- ALT:
 - o > 1xULN & ≤ 3xULN;
 - o > 3xULN & ≤ 5xULN;
 - o > 5xULN & ≤ 10xULN;
 - o > 10xULN & ≤ 20xULN;
 - o > 20xULN;
- AST or ALT:
 - o > 1xULN & ≤ 3xULN;
 - o > 3xULN & ≤ 5xULN;
 - o > 5xULN & ≤ 10xULN;
 - o > 10xULN & ≤ 20xULN;
 - o > 20xULN;
- Total bilirubin (TBL):
 - o > 1xULN & ≤ 2xULN;
 - o > 2xULN;
- Alkaline Phosphatase:
 - o > 1.5xULN;
- (AST or ALT) and TBL (all tests must be conducted within 72 hours):
 - o AST or ALT > 3xULN and TBL > 1.5xULN & ≤ 2xULN;
 - o AST or ALT > 3xULN and TBL > 2xULN;
- (AST or ALT) and ALP and TBL (all tests must be conducted within 72 hours):
 - o AST or ALT > 3xULN and ALP < 2xULN and TBL > 2xULN.

10.3.3.5 *Vital Signs*

Vital sign measurements will include blood pressure, heart rate, temperature, and respiratory rate. Height will only be measured at screening and weight will be measured as indicated in the schedule of events ([Appendix A](#), [Appendix B](#) and [Appendix C](#)). A change and percent change from baseline summary table, and a listing of measurement values by visit, will be provided for vital signs. Only scheduled visits will be included in change from baseline summary tables. All visits will be included in listings.

